To evaluate safety and efficacy of hyaluronic acid with sorbitol in athletes with overuse knee pain by comparing functional outcomes at short, medium and long term after treatment.

Specific Objectives

- To assess the safety and efficacy of hyaluronic acid with sorbitol in patients with sports-associated knee pain.
- To compare the clinical and functional results of patients with sport-associated knee pain after before and after treatment.

METHODS

Study Design

This research will be a cohort study, prospective and unidirectional direction.

Selection Criteria

- Patients with knee pain for more than 3 months
- Patients between 30 and 55 years old
- Patients without a history of previous knee joint surgery.
- Patients without chronic-degenerative diseases such as diabetes, hypertension, rheumatoid arthritis or other autoimmune diseases.
- Patients who perform impact social sports at least 3 times a week for more than 1 hour in the last 3 months prior to treatment.
- Patients without a history of allergies to non-steroidal anti-inflammatory drugs.
- Patients with no history of infection in or around the knee.

EXCLUSION CRITERIA

- Patients who cannot be categorized as social athletes.
- Patients with an associated sports injury that limits their sports practice.
- Patients who have a treatment associated with knee pain independent of that established in the study protocol.

ELIMITATION CRITERIA

- Patients who suffer from an injury or illness during the study that may limit their sports activity or who require an analgesic or anti-inflammatory treatment other than that established in the protocol.
- Patients who personally want to leave the study.
- Patients who did not have complete follow-up during the study.
- Patients who present an allergic or infectious reaction related to hyaluronic acid or prolotherapy or sepsis and antisepsis methods for infiltration.
- Patient with an allergic reaction to non-steroidal anti-inflammatory drugs.

VARIABLES

Variable	Operational Definition	Dimension	Variable type	Instrument	Indicator
Age	Time of life of any person	Without categories	Quantitative Discrete	Interview	Years
Gender	Biological and physiological characteristics that differentiate a man from a woman	Female Male	Qualitative Nominal	Interview	Gender
Body Mass Index	Score calculated by weight and height of a person.	Normal Overweight Obesity	Quantitative Discrete	Measuring tape Weighing machine	Weight in kg / Height in square meters

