To participants who initiate the study research will be applied the KOOS and IKDC scores, the results will be recorder in the collection data sheet. Appendix 2. Participants will be explored by physical exam focus on knee pathology, and also an echography knee scan

looking for non-overuse pain injuries. Coaching for sports activities will be explained for each patient in order to improve its own training techniques adding stretching exercises for previous and after training.

After treatment Group

After KOOS and IKDC scores were recorded two doses of Hyaluronic Acid plus sorbitol will be applied. Technique: On the examination table, the patient will lie down at supine position and the area of the knees to be infiltrated will be discovered. Asepsis of the knee region will be performed using an iodine and alcohol solution, the remaining synovial fluid in the joint will be extracted with a 10cc syringe then 4 milliliters of 80 mg of hyaluronic acid plus 160 mg of sorbitol will be applied (Synolis VA Aptissen S. A.) at the sub quadriceps level with a 22G x 32mm sterile needle. At the end of the infiltration, the needle will be removed, and the injection site will be covered with a small sticky-band, which can be thrown away after 20 minutes. It will be recommended to not make any kind of sports activity following the next 72 hours and apply ice therapy 3 times per day for over 20 minutes. Scores recorded data will be made at 15 days, then at 3 and 6 months.

Once the enrolling phase of the trial is concluded, statistical analysis will be made with Excel Office software for Windows, IBM SPSS and Prism.

Statistical analysis

Recorded data of the functional scores will be evaluated before and after treatment, also at 15 days, 3 and 6 months after hyaluronic acid supplementation.

Data analysis will be made by means standard deviation for numeric variables, also t-test for parametric and Wilcoxon Mann Whitney for non-parametric variables, a standard error of 95% is allowed. Differences in time will be calculated and group compared by Anova test. Variable correlation and association measures with relative risk and attributable risk with Fisher's test will be made with a confidence interval of 95%.

Ethical Implications

This research project will be developed after approval of the ethics and research Institutional committee.

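### The elimination criteria remove injected participants partly on outcome-related grounds, and no efficacy or safety set keeps them, so a completer-only result is a likely reading and would probably be too favourable

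*Combined protocol and SAP*

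**What the plan says.** The Elimination Criteria form a list separate from the selection and exclusion criteria, and they apply during the study, so they reach people already injected. The grounds are:

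- an injury or illness that may limit sport, or being patients "who require an analgesic or anti-inflammatory treatment other than that established in the protocol";
- personal withdrawal;
- "Patients who did not have complete follow-up during the study";
- "Patients who present an allergic or infectious reaction related to hyaluronic acid", a criterion that goes on to name prolotherapy and the antisepsis methods;
- an allergic reaction to NSAIDs.

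The first specific objective is "To assess the safety and efficacy of hyaluronic acid with sorbitol", so safety is an aim alongside efficacy. The design is a single prospective cohort, with KOOS and IKDC scored before treatment, at 15 days, and at 3 and 6 months.

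On data handling, the Statistical analysis section says "Recorded data of the functional scores will be evaluated before and after treatment" and at the three later visits. It names t-tests, Wilcoxon/Mann-Whitney, Fisher's test and "Differences in time will be calculated and group compared by Anova test". It gives no analysis set, no missing-data rule and no sensitivity analysis. The Sample Size section gives no allowance for eliminated participants.

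**The concern.** KOOS measures pain and sport function. IKDC asks about pain frequency, pain severity and the highest activity level. A participant whose knee still hurts enough to need an outside analgesic, or whose knee limits sport, tends to score badly and also meets an elimination ground. Other grounds, such as an unrelated illness, a personal decision to leave or an NSAID allergy, need not be linked to the scores.

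The efficacy evidence is the change from baseline, and there is no control arm in which the same selection would show. If those removed did worse on average, the reported improvement is too large and its confidence interval is off centre.

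For safety, a treatment-related allergic or infectious reaction is itself an outcome, yet it is a ground for elimination and no safety set is stated. If such participants also left the safety count, these reactions would read as zero whatever their true number.

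**Working it through.** **Inputs.** From the documents: 60 to 120 participants; four scoring times; 95% confidence. The range 60-120 cannot be rebuilt, because the sample size formula is given without values for p, q or e; it is used here only as n. The documents give no elimination rate, SD or correlation. Assumed: fraction eliminated f = 0.1 to 0.2; share of eliminations that is outcome-related s = 0.5, since the grounds are mixed; correlation between ground and change r = 0.3 to 0.5.

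**Step 1: what the text allows.** The complete-follow-up criterion can be applied only once follow-up is known. What it leaves is a set of completers. Nothing in the Statistical analysis section expressly restores the others. If the unspecified ANOVA were a classical repeated-measures ANOVA, it would also drop anyone missing one of the four scores.

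**Step 2: bias in SD of change.** If the fraction s·f with the lowest latent score is removed and the rest of the eliminations are random, bias b = r × φ(z)/(1 − s·f), where z is the s·f quantile of the normal distribution.

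- f = 0.1: s·f = 0.05, factor 0.109. r = 0.3 gives 0.033; r = 0.5 gives 0.054.
- f = 0.2: s·f = 0.10, factor 0.195. r = 0.3 gives 0.058; r = 0.5 gives 0.097.
- r = 0: no bias.

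**Step 3: coverage of the all-treated mean by the completers' 95% interval.** With m = n(1 − f) retained, coverage ≈ Φ(1.96 − b√m) − Φ(−1.96 − b√m).

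- Low end (f = 0.1, r = 0.3): n = 60, m = 54, b√m = 0.24, 94.3%; n = 120, m = 108, b√m = 0.34, 93.7%. Simulation (20,000 trials): 94.0% and 94.0%.
- High end (f = 0.2, r = 0.5): n = 60, m = 48, b√m = 0.68, 89.6%; n = 120, m = 96, b√m = 0.96, 84.1%. Simulation: 89.3% and 83.6%.

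**Step 4: a check without SD or correlation.** Let q be the mean change of those eliminated divided by that of those retained. Completer mean / all-treated mean = 1/[(1 − f) + f·q].

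- f = 0.1: q = 0 gives 1.111; 0.5 gives 1.053; 1 gives 1.000; 1.5 gives 0.952.
- f = 0.2: q = 0 gives 1.250; 0.5 gives 1.111; 1 gives 1.000; 1.5 gives 0.909.

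The error therefore vanishes if elimination is unrelated to outcome. It reverses if those removed had improved more, for example recovered athletes who skip visits.

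**Step 5: safety illustration.** An assumed 3 reactions among 60 injected is 5.0% (exact 95% CI 1.0% to 13.9%). If those three leave the count, it reads 0 of 57.

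**Step 6: does the remedy work?** Simulated with three follow-up visits, between-visit correlation 0.5-0.7, n = 120 and 4,000 trials. When elimination is half random and half driven by the score just recorded, the 6-month bias in completers is 0.058-0.079 SD (f = 0.1) and 0.105-0.142 SD (f = 0.2). Maximum likelihood on all recorded visits brings it to 0.001 SD or less in absolute value. When elimination is driven wholly by the next, unrecorded score, completers are biased by 0.16-0.18 and 0.30-0.32 SD, and maximum likelihood still leaves 0.09-0.11 and 0.18-0.22 SD.

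**Step 7: the trigger itself.** The analgesic criterion presupposes an analgesic or anti-inflammatory treatment set by the protocol, and NSAID allergy appears in both the selection and the elimination lists. Yet the treatment sections name no such drug. They give 72 hours without sport, stretching, "Coaching for sports activities will be explained for each patient" and "apply ice therapy 3 times per day for over 20 minutes". Prolotherapy is likewise mentioned in the reaction criterion but not described as a study treatment.

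**The case against.** Elimination is not defined. It could mean the end of participation with the data kept, and the sentence on recorded scores reads plainly as visit-by-visit use of whatever was collected. t-tests and Wilcoxon tests can run on available pairs, and repeated-measures ANOVA is never named. This stands: completer-only is a likely reading, not a stated rule. A reader might infer that recorded scores will be discarded, but the documents do not say so.

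The sizes rest wholly on assumptions. This also stands. A reader might take the worst case, in which every elimination is outcome-related (coverage down to 76% at n = 60 and 57% at n = 120 with f = 0.2 and r = 0.5). That does not fit a list of mixed grounds, so it is not the figure to rely on.

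Applying the reaction criterion requires someone to identify and attribute the reaction, so the event would be known. The available data sheet text stops at the treatment heading, so whether it has adverse-event fields cannot be judged. A reader might infer that reactions will go uncounted, but no text says this. The safety limb is conditional: nothing stated prevents it.

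Finally, natural change and coaching may matter more than a modest inflation in an uncontrolled study. That may be so, but it does not justify leaving the selection in place when recorded data can reduce it.

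**Conclusion.** The concern holds in a limited form. The protocol has stated rules that remove injected participants, some on grounds that can track the outcome, and no analysis set or missing-data rule that keeps them. The reported improvement would probably be too large. Certainty about the direction is a stronger claim that the documents do not support, because several grounds need not relate to the scores.

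In the mixed case assumed above, the bias is about 0.03-0.10 SD of change, with coverage of 94% to 89% (n = 60) or 94% to 84% (n = 120). The low end is minor; the high end is not. The safety consequence, a reading of zero for the listed reactions that lead to elimination, follows only if eliminated participants also leave the safety count. This should be fixed; confidence is medium, because the size cannot be found from the documents.

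**What to change.** - State that elimination does not remove recorded data.
- Main efficacy set: all injected participants with a baseline score. Use every recorded KOOS and IKDC visit in a repeated-measures mixed model with participant as random effect (knee within participant if both knees are scored), giving the change from baseline at each visit.
- Where follow-up is still open and consent allows, keep collecting the scheduled scores after an elimination event.
- Report completers as secondary, with the number and reason of every elimination.
- Add one sensitivity analysis that sets participants who took a non-protocol analgesic or anti-inflammatory, or were lost, to no improvement from baseline, or to their last recorded change if that is worse. Scores after analgesic use may credit the analgesic's relief to the product, and the mixed model reduces but does not remove bias from poor scores never recorded.
- Safety set: all injected participants, with allergic and infectious reactions kept in numerator and denominator.
- Reconcile the Elimination Criteria with the treatment sections on which analgesic or anti-inflammatory treatment, if any, the protocol sets, and on the mention of prolotherapy.

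Timing: enrolment was planned for June to October 2022, so the last 6-month visit falls about April 2023. The document is dated 01/12/2023, which is after that if read day-first and before it if read month-first. If follow-up had ended when the change is made, label these analyses post hoc. Scores never collected cannot be recovered.

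Cost: some wording, slightly more analysis and possibly a smaller reported improvement. Natural change and coaching remain uncontrolled.

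### Participants who need an analgesic outside the protocol are eliminated; if that takes them out of the analysis, the before-after improvement is probably overstated

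*Combined protocol and SAP*

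**What the plan says.** All references are to the combined protocol and SAP.

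- **Elimination Criteria, first bullet.** It opens with "Patients who suffer from an injury or illness during the study that may limit their sports activity" and then adds those "who require an analgesic or anti-inflammatory treatment other than that established in the protocol".
- **Elimination Criteria, other bullets.** One removes "Patients who did not have complete follow-up during the study". Another removes a "Patient with an allergic reaction to non-steroidal anti-inflammatory drugs".
- **Selection Criteria.** Entry is limited to "Patients without a history of allergies to non-steroidal anti-inflammatory drugs".
- **Exclusion Criteria.** These bar "Patients who have a treatment associated with knee pain independent of that established in the study protocol". This again refers to a treatment set by the protocol without naming a drug.
- **Before treatment Group and After treatment Group.** The care described is coaching, stretching, the injection, 72 hours without sport, and advice to "apply ice therapy 3 times per day for over 20 minutes". No analgesic or anti-inflammatory appears.
- **Statistical analysis.** "Recorded data of the functional scores will be evaluated before and after treatment", with further scores at 15 days, 3 months and 6 months. No analysis set and no missing-data rule is given.
- **Appendices 1 and 2.** The IKDC and KOOS forms both ask directly about knee pain.
- **Appendix 3.** The text available of the data sheet stops at its treatment heading, and the consent pages were not available.

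**The concern.** Participants enter with more than three months of knee pain, and the outcome is scored partly on pain. Persisting knee pain is one plausible reason to need an analgesic. A rule that removes people for that need, after treatment, tends to remove those who improved least.

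The study follows one treated cohort; its before and after groups are the same people at different times. The result is the mean change in whoever is retained, and there is no second arm in which similar removals could offset the effect. The bias would favour the product and would not shrink with more participants.

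The undefined exemption adds a practical problem. If staff cannot tell which drug is permitted, they may apply the rule differently from one participant to the next.

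**Working it through.** **Plan's own figure.** The plan gives none on this point. Its only design figure is 60 to 120 participants. The sample size formula comes without values for p, q or e, so that range cannot be reproduced. The argument below does not depend on it, except that 60 and 120 serve as the enrolled numbers.

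**Is removal from the analysis stated?** No. It is inferred from two things: the rule is called elimination, and an adjacent bullet eliminates people for incomplete follow-up, which makes most sense if the dataset is restricted to completers. Someone eliminated for analgesic need and not followed further would also fall under that bullet.

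**Size of the inflation.** Let p be the share of enrolled participants removed, m the mean change in those retained, and d the amount by which the removed change less, in SDs of change among those retained.

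Mean(all) = (1 − p)·m + p·(m − d) = m − p·d, so inflation = p·d.

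The documents give neither p nor d; all values here are assumptions. The chance of a falsely significant improvement uses a one-sample t-test on change, two-sided 5%, upper tail, with a true mean change of zero in all treated and noncentrality p·d·√(n retained). The nominal value is 2.5%.

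| p | d | Inflation (SD) | n retained (of 60 / of 120) | Chance (60 / 120 enrolled) |
|---|---|---|---|---|
| any | 0 | 0 | – | 2.5% / 2.5% |
| 0.10 | 0.25 | 0.025 | 54 / 108 | 3.8% / 4.4% |
| 0.10 | 0.5 | 0.05 | 54 / 108 | 5.5% / 7.4% |
| 0.20 | 0.5 | 0.10 | 48 / 96 | 10.0% / 16.1% |
| 0.20 | 1.0 | 0.20 | 48 / 96 | 27.3% / 49.2% |

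Reference row: 0.10 × 0.5 = 0.05; noncentrality 0.05 × √54 = 0.37 and 0.05 × √108 = 0.52. The row with d = 0.25 corresponds to half of those removed having a 0.5 SD deficit and half none. The last row is an extreme corner.

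**Cross-check by another model.** Suppose analgesic need follows a normal latent variable, and change has correlation ρ with not needing the drug. The inflation is then ρ·φ(z_p)/(1 − p). At p = 0.10 this gives 0.06 SD for ρ = 0.3 and 0.10 SD for ρ = 0.5. The 0.05 SD reference case is therefore not exaggerated.

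**Does keeping the scores repair it?** In simulation of the reference case (200,000 samples), the retained-only analysis gave 5.6% at 60 enrolled and 7.4% at 120. Including everyone gave 2.4% at both. That assumes complete scores and no analgesic relief in the restored scores. If the drug raises those participants' change, and the target is change without the drug, the all-scores analysis gives approximately:

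| Assumed relief (SD) | 60 enrolled | 120 enrolled |
|---|---|---|
| 0 | 2.4% | 2.4% |
| 0.25 | 3.7% | 4.5% |
| 0.5 | 6% | 8% |
| 0.75 | 8% | 12% |

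At 0.5 SD of relief, keeping the scores does no better on that target than dropping the participants. It does meet a different target: change in all treated participants regardless of analgesic use. The target therefore has to be stated.

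**The case against.** The best case against the point is that it depends on several conditions and the effect is modest.

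- **Scope of the bullet.** It opens with a new injury or illness, so the drug clause might apply only in that setting. This reading is possible. The wording more naturally makes drug need a separate ground.
- **Meaning of elimination.** A reader might infer that the plan commits to dropping these participants from the analysis. It does not say so, and the bias is conditional on it. But a plan that leaves the matter open lets the choice be made after results are seen.
- **Reason for the drug.** Analgesics taken for an unrelated cause, or for brief soreness after injection, need not relate to change and would then add no bias. This stands.
- **The permitted drug.** A reader might infer that the protocol allows no drug at all. The documents do not support that: the NSAID-allergy criteria suggest one was intended, and some pages are unavailable. Nor does the bias depend on it, since any drug outside a permitted list still triggers elimination.
- **Effect on the conclusion.** If the true change were 0.5 SD (assumed), the chance of a significant result at 60 enrolled would be 96.8% without the rule and 97.8% with it (10% removed, 0.5 SD deficit); at 120 it would exceed 99.9% either way. The significance test would hardly move. The estimate would still be too high by 0.05 SD.
- **Relief in retained scores.** This stands in full and shapes the fix. Leaving these participants out does not give the result free of analgesic relief; it gives the selected result that is in question.

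**Conclusion.** The point holds in conditional form. The rule is written, the text available names no permitted drug, and the analysis set is undefined. If eliminated participants leave the analysis, the mean improvement is probably overstated, because the ground for removal is related to a pain-scored outcome and there is no control group.

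The size cannot be obtained from the documents. It is 0.05 SD with an assumed 10% removed and a 0.5 SD deficit, and zero if analgesic need is unrelated to change. Among the cases tried, it reaches 0.20 SD only with 20% removed and a 1.0 SD deficit together. The false-significance figures use zero true change as a benchmark; since everyone also receives coaching and stretching, they are not a forecast.

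Two stronger readings should be avoided. The documents do not show that any observed improvement would be an artefact of this rule. Nor does keeping the scores guarantee a return to 2.5%; that is a best case with complete scores and no analgesic relief. The change is worth making, with medium confidence.

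**What to change.** 1. State the target: the main analysis estimates change in all treated participants regardless of analgesic use.
2. Do not remove participants from the analysis for analgesic need, or for incomplete follow-up that results from it. Include all their collected scores.
3. If the planned ANOVA is repeated-measures, fit it as a mixed model, so that a missed visit does not drop the participant. This is valid if missingness is explained by the observed scores.
4. Add a sensitivity analysis that counts participants who needed an outside analgesic for knee pain as non-responders from that point, for example with later scores set to baseline. This treats them as unchanged, so it is lenient for anyone who got worse.
5. The analysis without these participants may be shown, labelled as a selected subset.
6. Report eliminations by reason and visit. Name any permitted analgesic or NSAID (a decision for the clinical lead), and record analgesic use at any remaining visits.

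**Cost.** One clause reworded, one bullet qualified, a sentence on the target, one table and one sensitivity analysis. The reported improvement may be slightly smaller, and the main estimate will include some analgesic relief.

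**Timing.** Enrolment to October 2022 plus 6 months ends about April 2023. If the version date 01/12/2023 is 1 December, no visits remain and only collected scores can be restored. If it is 12 January, 6-month visits remain for those treated after about 12 July 2022, and 3-month visits for those treated after about 12 October 2022.
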